Study title: Clinical Evaluation of Safety and Efficacy of Radio Frequency (Forma Eye) Treatment for Dry Eye Disease Due to Meibomian Gland Dysfunction

Date: May 2022

Identifiers: NCT04120584

Unique Protocol ID: DO609175A

Study Title	Clinical Evaluation of Safety and Efficacy of Radio Frequency (Forma Eye) Treatment for Dry Eye Disease Due to Meibomian Gland Dysfunction
Protocol Number	DO609175A
Sponsor	InMode Ltd.
Study Design	Prospective, open label, clinical study.
Planned Study Duration	Study duration including recruitment will be up to 12 months.
Investigational Device	Forma Eye handpiece
Planned Sample Size	At least 40 adult subjects with symptoms of evaporative dry eye/MGD
Subject Selection	Investigator will determine patient's eligibility to participate in the study according to inclusion/exclusion criteria.

Treatment and Duration	
Eligible subjects will receive up to 3 treatments (2-3 weeks interval) with the Forma Eye Applicator according to the study protocol.
 
Site#1:
 
First 5 subjects will receive up to 3 treatments (2-3 weeks interval)
 
Another 15 subjects will receive 1 treatment
 
Site#2:
 
15 subjects will receive 1 treatment
 
Site#3:
 
5 subjects will receive 1 treatment
 
The subject will return for 3 follow up visits: four weeks (4wk FU), 12 weeks (12wk FU), twenty-four weeks (24wk FU) after the last treatment.

Study Objectives	
The objective of this trial is to evaluate the safety and efficacy of the Forma Eye Applicator for Symptoms of Dry Eye Disease Due to Meibomian Gland Dysfunction

Secondary Objective	
The secondary objective of this study is subject satisfaction, as measured with a self-assessment questionnaire and a rating of device and procedure related adverse events.

Main Endpoints	
Primary objectives will be measured using the next efficacy endpoints:
 
 
• Mean change from baseline to prior to second, third treatments as well as four weeks (4wk FU), 12 weeks (12wk FU), twenty-four weeks (24wk FU) in Standardized Patient Evaluation of Eye Dryness (SPEED)
 
• Mean change from baseline to prior to second, third treatments as well as four weeks (4wk FU), 12 weeks
 

	
(12wk FU), twenty-four weeks (24wk FU) in Ocular Surface Disease Index (OSDI)
 
 
• Improvement measurements using ocular surface fluorescent staining. NEI grading scheme grading for ocular surface staining score will be used in this study.
 
• Changes from baseline to prior to second, third treatments as well as four weeks (4wk FU), 12 weeks (12wk FU), twenty-four weeks (24wk FU) in Meibomian Gland Score (MGS), as assessed by a masked rater
 
• Changes from baseline to prior to second, third treatments as well as four weeks (4wk FU), 12 weeks (12wk FU), twenty-four weeks (24wk FU) in Tear Break-Up Time (TBUT).
 

Secondary Endpoints
	
 
• Subject assessment of improvement based on 0 - 4-point Likert scale at four weeks (4wk FU), 12 weeks (12wk FU), twenty-four weeks (24wk FU) follow up visits. Improvement assessment will be performed independently by the subject himself on the following 0-4 points Likert scale questionnaire (Global Aesthetic Improvement Scale): 4 = Significantly marked improvement; 3 = Marked improvement; 2 = Moderate improvement; 1 = Slight improvement; 0 = No difference
 
• Subject assessment of satisfaction will be filled-out by subjects only using 5-points Likert scale at four weeks (4wk FU), 12 weeks (12wk FU), twenty-four weeks (24wk FU) follow up visits: +2 = Very satisfied; +1 = Satisfied; 0 = Indifferent; -1 = Disappointed; -2 = Very disappointed
 
• Safety assessment:
 

	
 
○ The number, severity and type of any adverse event recorded throughout the study and post treatment (immediate and delayed response)
 
○ Discomfort assessment during the treatment using NSR scale
 

Statistical Methods	Descriptive statistics will be used to present changes in the assessments along the study course.

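### The subject-rated improvement endpoint is specified on a scale named as aesthetic, with no rated attribute stated, so its scores cannot be read as dry-eye improvement

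*Combined protocol and SAP*

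**What the plan says.** All of the relevant text is in the synopsis of the combined protocol and SAP.

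- **Study Objectives.** The trial sets out to "evaluate the safety and efficacy of the Forma Eye Applicator for Symptoms of Dry Eye Disease Due to Meibomian Gland Dysfunction", and no other main objective is given.
- **Secondary Objective.** "The secondary objective of this study is subject satisfaction, as measured with a self-assessment questionnaire", together with a rating of adverse events related to device and procedure.
- **Main Endpoints.** Two are symptom questionnaires: "Standardized Patient Evaluation of Eye Dryness (SPEED") and the OSDI. The other three are ocular surface staining, the meibomian gland score and tear break-up time.
- **Secondary Endpoints, improvement item.** "Subject assessment of improvement based on 0 - 4-point Likert scale at four weeks (4wk FU"), and again at 12 and 24 weeks. The subject completes it independently. The instrument is given as a "Likert scale questionnaire (Global Aesthetic Improvement Scale"), with these levels: "4 = Significantly marked improvement; 3 = Marked improvement; 2 = Moderate improvement; 1 = Slight improvement; 0 = No difference".
- **Secondary Endpoints, satisfaction item.** "Subject assessment of satisfaction will be filled-out by subjects only using 5-points Likert scale", at the same three visits, scored from +2 to -2.

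The Statistical Methods entry plans descriptive statistics for the assessments. The Data Analysis section adds comparison tests where they apply. Neither mentions the improvement item by name.

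**The concern.** The scale's name points to appearance, while the trial is about dry eye. A global rating of improvement made by the subject is an obvious result to cite as evidence that patients felt better, particularly in an open-label study for which the synopsis mentions no control group. That use requires that subjects were rating their dry eye, and the plan does not say so.

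If some subjects rate how the eye area looks, one with unchanged dryness could truthfully give a high score, and one with real relief but no visible change could truthfully give 0. A disagreement between this item and SPEED or OSDI would then have no clear interpretation. With three sites, staff may also explain an undefined item differently.

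**Working it through.** The plan states no figure for this endpoint and the point needs no arithmetic. The check is to compare the four pieces of text that could tell a subject, a site or a reader what is being rated.

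1. **Endpoint wording.** It is the subject's assessment of improvement. It names neither appearance nor dry eye, and gives no reference time for the comparison.
2. **Answer levels.** There are five, from 0 to 4. All are generic grades of improvement, except the lowest, which is no difference. None names an attribute.
3. **Instrument name.** It is the only part of the endpoint's own text that names a construct, and the construct is aesthetic improvement.
4. **Objectives and other endpoints.** The main objective is dry-eye symptoms, and all five main endpoints are dry-eye measures. The secondary objective is satisfaction and adverse events. Nothing else in the plan concerns appearance.

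Item 3 therefore conflicts with item 4, and items 1 and 2 do not resolve the conflict. The question put to the subject is not shown, which leaves three possibilities:

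| If the form asks about | Then |
|---|---|
| appearance | the endpoint does not measure dry-eye improvement |
| dry eye | the endpoint is useful, but the plan names the wrong instrument and a report under that name would mislabel it |
| improvement, unspecified | each subject chooses the attribute, and the score is a mixture in unknown proportion |

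In every row the plan needs the same correction: state the attribute and remove the name.

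**Extent.** The synopsis lists two subject-rated Likert items as secondary endpoints, improvement and satisfaction. One of the two is affected, at all three of its visits (4, 12 and 24 weeks). The SPEED and OSDI changes are planned at those same visits and are untouched.

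**Size in points.** None can be derived. It would need the share of subjects rating appearance and how their ratings differ from their dry-eye change, and the documents give neither. The two kinds of subject described above move the mean in opposite directions, so even the sign is open.

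**A related feature of the scale.** It has no level for worsening, whereas the satisfaction scale does have negative levels. A question asking how symptoms have *changed* would not fit these answers, which limits how the item can be reworded.

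**The case against.** The strongest reply is that the argument rests on a name in parentheses. The endpoint and its answer levels never mention appearance, and the author may simply have borrowed a familiar scale name for generic anchors. Nothing shows that the subject sees the name. Subjects enrol with dry-eye symptoms in a study titled as a dry-eye treatment evaluation, and are assessed with SPEED and OSDI at the same visits, so the context points to dry eye. The available text is a synopsis and a short analysis section, and the questionnaire itself may carry a clear question. Finally, the item is secondary, and no passage proposes it as proof of symptom relief.

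Much of this stands. A reader might infer that the trial asks subjects about their looks and that the answers have no bearing on the objective. The documents do not support that: no question is shown, the anchors are neutral, and a global rating of dry-eye improvement would bear directly on efficacy. It would equally be wrong to declare all completed forms aesthetic ratings.

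Context does not repair the specification, however. It may guide some subjects, but the plan still names an instrument for a construct that no objective contains, and nothing in the available text redirects it to dry eye. Nor does the satisfaction item fill the gap, since satisfaction is a different construct.

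**Conclusion.** The point holds in limited form. The instrument is named for a construct outside the trial's objectives and the rated attribute is undefined. As specified, the 4-, 12- and 24-week improvement scores cannot support a statement that subjects felt their dry eye improve.

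The consequence stops at this secondary endpoint. SPEED and OSDI still address the symptom objective, and no main endpoint or safety assessment depends on the item. It is a worthwhile, inexpensive correction and does not threaten the trial's main conclusions.

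The conclusion rests on the available text showing everything the plan says about this item. If the full form carries a dry-eye question, the problem reduces to a wrong label. The inference that subjects were in fact asked about appearance goes further than the documents do.

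**What to change.** **In the plan and on the form.** Remove the aesthetic scale name from Secondary Endpoints and state the question. It should name dry-eye symptoms, fix the reference time and fit the existing answer levels, for example: *Compared with before your first treatment, how much have your dry eye symptoms improved?* If the sponsor prefers to ask how symptoms have changed, a worsening level must be added. Report the item as subject-rated dry-eye symptom improvement.

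**For forms already completed.** Check the question that was actually asked.
- If it was about dry eye, state it in the report and correct the label. No data are lost.
- If it was about appearance, or the attribute was not specified, report those ratings separately and do not cite them as dry-eye efficacy.

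**Cost.** One line of endpoint and questionnaire wording, with no added visit or procedure. The drawback is that ratings from differently worded forms cannot be pooled, so a change partway through would divide the data for this endpoint.

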## DATA ANALYSIS

Statistical analysis of all major factors will be performed to determine quantitatively the treatment efficacy.

The data will be analysed by the Sponsor using basic descriptive statistics, as well as comparison tests, where applicable. Treatment-related complications will be monitored and reported; if applicable, their incidence rate will be calculated and analysed for any relationship to treatment parameters.

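### The subject improvement scale has no answer for worsening, so worse and unchanged cannot be told apart and a mean score is biased upward whenever anyone worsens

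*Combined protocol and SAP*

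**What the plan says.** The synopsis, under Secondary Endpoints, lists "Subject assessment of improvement based on 0 - 4-point Likert scale at four weeks (4wk FU), 12 weeks (12wk FU), twenty-four weeks (24wk FU") among the secondary endpoints. The rating comes from the subject alone, and the permitted answers are "4 = Significantly marked improvement; 3 = Marked improvement; 2 = Moderate improvement; 1 = Slight improvement; 0 = No difference". No answer lies below 0, and nothing in the documents says how to record a subject whose condition has deteriorated.

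The next item in the same list, satisfaction, is collected at the same three visits on a scale with negative answers: "2 = Very satisfied; +1 = Satisfied; 0 = Indifferent; -1 = Disappointed; -2 = Very disappointed" (the top score being +2).

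On analysis, the synopsis says "Descriptive statistics will be used to present changes in the assessments along the study course". The Data Analysis section says "basic descriptive statistics, as well as comparison tests, where applicable". Neither states whether the improvement item will be summarised as a mean, a percent improved or a full distribution. The design is given as "Prospective, open label, clinical study", and no control arm is described.

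**The concern.** A rating that can only be zero or positive can only average zero or more. Natural fluctuation, with some subjects feeling better and some worse, would appear on this item as improvement. The answer 0 pools unchanged and worsened subjects, so the item cannot separate net benefit from movement in both directions.

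The planned analysis does nothing to limit this. A mean, a percent improved, or a test of the mean against 0 would all fit the text, and none would reveal the worsened subjects. Because no control arm is described, there is also no comparison group scored with the same floor against which to judge how high the score would be without any effect.

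**Working it through.** The plan states no figure for this endpoint, so there is nothing to reproduce. The direction follows from algebra. The size needs assumptions, which are stated below.

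**Inputs from the documents.** The scale is 0 to 4 with 0 as the lowest answer. The planned sample is at least 40 (the site numbers 5 + 15 + 15 + 5 sum to 40).

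**Direction.** Let a share w of subjects worsen, with average true score -s (s > 0) on a scale extended below 0, and let a share p improve.
- Worsened subjects recorded as 0: bias of the mean = w × s, which is positive whenever w > 0 and zero when nobody worsens.
- Worsened subjects leave the item blank: the mean is taken over the others only and exceeds the true mean. Percent improved becomes p/(1 - w) instead of p.
- Worsened subjects recorded as 0, percent improved on the full denominator: the figure stays at p, but the share w is invisible.

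**Simple count example (assumed).** Of 40 subjects, 10 are unchanged, 8 worsen by 1 point and 22 improve by 2 points on average.
- True mean: (22 × 2 - 8 × 1)/40 = 36/40 = 0.90.
- Recorded as 0: 44/40 = 1.10, a bias of 8/40 × 1 = 0.20.
- Left blank: 44/32 = 1.375, a bias of 0.475. Percent improved moves from 22/40 = 55.0% to 22/32 = 68.8%.

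**Range under a distributional model (assumed).** Perceived change is normal with mean μ and SD 1.0, 1.5 or 2.0. It is cut at ±0.5, ±1.5, ±2.5 and ±3.5 into scores -4 to +4, and negative scores are then set to 0. The recorded mean is the sum of P(change > c) over c = 0.5, 1.5, 2.5 and 3.5. For μ = 0 and SD 1.0 this is 0.3085 + 0.0668 + 0.0062 + 0.0002 = 0.382.

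| True mean μ | Quantity | SD 1.0 | SD 1.5 | SD 2.0 |
|---|---|---|---|---|
| 0 | Recorded mean (all of it bias) | 0.382 | 0.586 | 0.774 |
| 0 | Share improved (equals share worse) | 31% | 37% | 40% |
| 0 | Worsened, of 40 | 12.3 | 14.8 | 16.1 |
| 0 | Worsened as share of 0 answers | 45% | 59% | 67% |
| 0 | Mean among responders, if worsened leave blank | 0.552 | 0.929 | 1.292 |
| 0 | Percent improved, if worsened leave blank | 45% | 59% | 67% |
| -0.5 (half worse) | Mean on the two-sided scale | -0.500 | -0.496 | -0.477 |
| -0.5 | Recorded mean | +0.183 | +0.370 | +0.557 |
| +1 | Mean on the two-sided scale | 1.000 | 0.989 | 0.948 |
| +1 | Recorded mean | 1.073 | 1.206 | 1.332 |
| +1 | Bias | 0.073 | 0.218 | 0.385 |
| +1.5 | Bias | 0.024 | 0.118 | 0.254 |
| +2 | Bias | 0.006 | 0.059 | 0.161 |

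The share of 0 answers that come from worsened subjects is w/(w + u), where u is the share unchanged. For μ = 0 and SD 1.0 this is 0.309/(0.309 + 0.383) = 0.446.

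**The case against.** The plan reserves mean change for SPEED and OSDI and does not commit to a mean for this item. A full category table, the natural display for a five-level ordinal answer, would be consistent with the text and has no mean to bias. Percent improved is not numerically biased when worsened subjects answer 0. That they would leave the item blank is conjecture, and the largest figures depend on it. If most subjects improve clearly, the bias is small. Deterioration can also register in SPEED, OSDI, MGS, TBUT, satisfaction and adverse events. Finally, satisfaction is not an exact parallel, since an unchanged subject may well be disappointed.

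Most of this stands as a limit on severity and size. It does not remove the fault. A category table on the present form would still merge worse with unchanged, because the information is never collected. The other endpoints can show deterioration, but they do not make this item interpretable. The satisfaction scale is offered only as evidence that two-sided answers are practical at these visits, and it does show that.

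**Conclusion.** The concern holds. The improvement item, as defined, cannot distinguish a worsened subject from an unchanged one, and any mean of it is biased upward whenever at least one subject worsens. That direction needs no assumption.

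The size cannot be derived from the documents. It rests on an assumed mean, SD and normal shape. With worsened subjects scored 0, the modelled bias runs from about 0.01 points (true mean +2, SD 1.0) to 1.03 points (true mean -0.5, SD 2.0: 0.557 + 0.477). It is small if nearly everyone improves. It is largest when the effect is weak or absent, and at a true mean of -0.5 the recorded mean has the wrong sign.

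This is a moderate limitation of one secondary endpoint, affecting how the item may be read. It does not affect the trial's overall ability to detect deterioration. It should be fixed because the remedy is cheap.

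**What to change.** **If the form can still be changed:** add worsening categories, for example -1 to -4 mirroring the existing anchors, and word the item as change in dry eye symptoms since before treatment, so that both directions have a clear reference point. State in the analysis section that the full category distribution will be reported at 4, 12 and 24 weeks, including percent worse and number missing, with all assessed subjects in the denominator. The cost is one revised questionnaire item and case report form field, and a score that may look less favourable.

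**If data are already on the 0 to 4 form:** report every category count and the number missing at each visit, and state that worsening could not be measured on this item. Do not test the mean against 0 or describe it as net improvement. For subjects who answered 0 or left the item blank, tabulate SPEED and OSDI change from baseline at the same visit, so that readers can see how many had worsened on those measures. The cost is one extra table from data the plan already collects.

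### With no longitudinal model or missing-data method in the plan, the 24-week change could be overstated if poor responders are lost selectively

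*Combined protocol and SAP*

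**What the plan says.** The synopsis row on Statistical Methods reads "Descriptive statistics will be used to present changes in the assessments along the study course". The DATA ANALYSIS section says that the sponsor will analyse the data using "basic descriptive statistics, as well as comparison tests, where applicable", and gives a quantitative determination of efficacy as the aim. No test is named.

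Four of the five main endpoints (SPEED, OSDI, MGS, TBUT) are changes from baseline at each visit, including 4, 12 and 24 weeks. The staining endpoint names no visits. On follow-up, Treatment and Duration says: "The subject will return for 3 follow up visits: four weeks (4wk FU), 12 weeks (12wk FU), twenty-four weeks (24wk FU) after the last treatment".

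The design is "Prospective, open label, clinical study", with no control arm described. The planned size is "At least 40 adult subjects with symptoms of evaporative dry eye/MGD". The site allocations add up to it: 5 + 15 + 15 + 5 = 40. Only the first 5 subjects at site 1 may have up to three treatments; the other 35 have one.

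The text gives no longitudinal model, analysis set, missing-data rule or expected dropout.

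**The concern.** A descriptive mean change at a visit can use only subjects with a value at that visit. Without a missing-data rule, the 4-, 12- and 24-week means may therefore describe three different groups of subjects. The unnamed comparison tests would not alter that.

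If subjects who benefit little are less likely to return, the 24-week group is a favourable selection and its mean change exceeds that of all treated subjects. In a controlled trial, similar loss in both arms might offset some of this; here nothing does. The 24-week change is also the figure on which any claim of a lasting effect would rest. The 4- and 12-week values of subjects who leave later carry information about what was lost, and a visit-by-visit mean ignores it.

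**Working it through.** The plan has no power, SD, effect-size or dropout figure, so there is nothing of its own to reproduce. The question is how far the mean of those observed at 24 weeks can differ from the mean of all treated subjects.

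**Inputs from the documents:** 40 subjects; visits at baseline, 4, 12 and 24 weeks.

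**Assumptions:** true improvement 0.6 SD of change at each follow-up visit; correlation ρ between changes at different visits 0.5 to 0.7; loss d by week 24 of 10%, 20% or 30%; everyone seen at week 12; logistic dropout with slope s per SD of poorer response. s = 0.5 is called weak (odds of loss multiplied by exp(0.5) = 1.65 per SD) and s = 1.5 strong (exp(1.5) = 4.5).

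**Step 1, a simple case.** If all lost subjects had zero true change, the observed mean is the all-treated mean divided by (1 − d). The overstatement is 1/(1 − d) − 1, which is 11%, 25% and 43% at d = 0.1, 0.2 and 0.3.

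**Step 2, loss driven by the week-12 change.** Let Z be the standardised week-12 change, larger meaning poorer, and P(Z) = 1/(1 + exp(−(a + sZ))) the chance of being lost, with a set so that P averages d. Those observed at week 24 had a week-12 change better by m = −∫ z φ(z)[1 − P(z)] dz / (1 − d) SD. Their 24-week change is better by ρm, so the overstatement is ρm/0.6.

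| s | d | m | ρ = 0.5 | ρ = 0.7 |
|---|---|---|---|---|
| 0 | any | 0 | 0% | 0% |
| 0.5 | 10% | 0.049 | 4% | 6% |
| 0.5 | 20% | 0.096 | 8% | 11% |
| 0.5 | 30% | 0.143 | 12% | 17% |
| 1.5 | 10% | 0.122 | 10% | 14% |
| 1.5 | 20% | 0.227 | 19% | 26% |
| 1.5 | 30% | 0.327 | 27% | 38% |

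Simulated 40-subject trials give roughly 3% to 17% for weak and 10% to 38% for strong dependence, which agrees apart from a small difference at the low end. With the sign of s reversed (good responders lost), the bias has the same size and the opposite sign.

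**Step 3, the repeated-measures model in the same settings.** When loss depends on the week-12 change, the likelihood estimate is within about 1.5% of the truth. When loss is random, both methods are unbiased. When loss depends on the unseen 24-week value, ρ in step 2 becomes 1: the observed mean is too high by 0.049/0.6 = 8% up to 0.327/0.6, about 54%. The model is then still too high by about 4% to 39%.

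A second set of simulations used correlations of 0.3 to 0.7 between scores (exchangeable or AR(1)), s = 1.5, and loss tied either to the last observed change or to the change at the missed visit. In the first case the observed mean was 8% to 43% too high and the model within about 1.5%. In the second, the observed mean was 13% to 64% too high and the model 8% to 29%, so 37% to 61% of the bias was removed.

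**Step 4, a zero-change sensitivity analysis.** With strong dependence on the unseen value, its overstatement is (1 + m/0.6)(1 − d) − 1:

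- d = 10%: 1.203 × 0.9 = 1.08, so 8%
- d = 20%: 1.378 × 0.8 = 1.10, so 10%
- d = 30%: 1.545 × 0.7 = 1.08, so 8%

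If loss is random it understates the change by d, that is 10% to 30%. It is a check on the result rather than an estimate.

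**The case against.** The strongest reply is that the documents contain no evidence of selective loss. They give no rate, reason or pattern; random loss gives no bias, and loss of subjects who feel well would make the 24-week figure too small. This stands. A reader might infer that the late effect is inflated, but the documents support only that it could be.

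Nor does the plan say that only attenders will be averaged. That is the default result of a descriptive mean with no missing-data rule. The supplied text is also short and refers to eligibility criteria that it does not reproduce, so a fuller text might cover withdrawals. The point concerns the two places where the method is stated, and neither does.

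The larger percentages need a steep slope. At 20% loss, s = 0.3 gives only 5% to 7%. Even the strong case at 20% loss is 0.19 × 0.6 = 0.11 to 0.26 × 0.6 = 0.16 SD, below the standard error of a 32-subject mean (1/√32 = 0.18 SD). That is fair on size. Unlike sampling error, however, the bias is not reflected in an interval around the observed mean.

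A reader might also infer that a mixed model largely removes the problem. It does so only when loss is explained by values already seen, and the near-zero bias in step 3 follows from assuming exactly that.

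Finally, a plan that sets out to be descriptive, with no stated hypothesis, might be thought to need no model. But the plan also aims to quantify efficacy. The absence of a dropout figure is no reason to leave the method open, since it should be fixed before losses are known.

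**Conclusion.** The point holds in conditional form. The plan has no longitudinal model and no missing-data method for changes followed to 24 weeks, and there is no control arm to offset selective loss. Whether the 24-week change would be overstated, and by how much, cannot be read from the documents. The range runs from about 0% (random loss) to 38% (strong dependence on the week-12 change, 30% loss, correlation 0.7). It is larger still if loss follows the unseen 24-week value, and negative if good responders leave. Every percentage depends on the assumed effect, correlation, loss and slope.

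A likelihood-based repeated-measures model is the better default: it corrects loss that depends on observed values and, with complete data, returns essentially the same visit means. Because it is only a partial remedy otherwise, it needs a sensitivity analysis beside it. This is an improvement that should be made; it is not evidence that the study's result would be wrong.

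**What to change.** Add to DATA ANALYSIS:

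> For SPEED, OSDI, MGS and TBUT, scores at baseline, 4, 12 and 24 weeks will be analysed in all treated subjects with a likelihood-based mixed model for repeated measures (baseline included as a response, visit as fixed effect, unstructured covariance), and mean change from baseline at each follow-up visit will be given with a 95% CI. Assessments before the second and third treatments will be summarised separately. The number observed and their baseline mean will be shown at each visit. As a sensitivity analysis, subjects missing at 24 weeks will be given zero change.

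Treating baseline as a response keeps subjects with no follow-up visit in the model. Separating the pre-second and pre-third treatment assessments matters because only the first 5 subjects can have them, too few to support their own variances and covariances. The model pools the two treatment schedules, and the text should say so. The staining endpoint needs named visits before it can be analysed in the same way.

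The cost is slightly more analysis work with standard software and no extra visits or data, and possibly a less favourable 24-week figure. The model does not make up for the lack of a control arm.
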